5.6 STRATEGIES FOR RECRUITMENT AND RETENTION

The protocol will study 32 healthy individuals. Participants who are withdrawn or drop out from the study will be replaced. NIH employees who are not members of the BNU will be allowed to participate. Based on current experience, the anticipated non-completion rate is 22%, due to screen failures, individual characteristics making stimulation impossible, such as very high motor evoked potential threshold, non-removable hair braiding, and other issues discovered after consenting.

Healthy participants will be recruited from the pool of individuals self-referring to the study directly and via the NIH Clinical Research Volunteer Program. Although NIH employees will be allowed to participate, no direct solicitation of employees/staff by supervisors or co-workers will take place. Any recruitment material will be IRB approved. Participants who indicate interest will be pre-screened by phone. Pre-screening questions are listed in Appendix B.

It is possible that some participants will miss a session. If this occurs, and the participant is still willing to participate, they will be rescheduled. If a participant no longer wishes to continue with the study, a new participant will be recruited for the full study. If they have data from one experiment, those data may be included in analysis for that experiment but excluded from any comparisons across experiments.

It is possible that technical problems may arise. If this occurs, and the participant is willing to continue with the study, they will be rescheduled.

When data from a subject are not usable due to noise or other technical problems, a new participant will be recruited for the full study to achieve a sample of 32 complete subjects.

5.6.1 Costs

N.A.

5.6.2 Compensation

All participants will be compensated for time and research-related inconveniences in accord with NIH guidelines as follows:

Compensation for time

First hour	\$20
Additional hours	\$10

Compensation for inconveniences

Participants will be paid \$10.00 per one Inconvenience Unit (IU).

fMRI testing (4 IU)	\$40
TMS testing (4 IU)	\$40
EEG testing (2 IU)	\$20

Abbreviated Title: Task-dependent TMS and memory

Version Date: 11.15.22

Behavioral Tasks (2 IU)	\$20
Pregnancy Test (1 IU)	\$10

Payment (check) will be mailed to participants after they complete the protocol, or by direct deposit if available. If participants are unable to finish the study, they will be paid for the portion of the study completed. No reimbursement for travel or escort fee will be provided.

Employees and staff who participate during work hours must have permission from their supervisor. NIH employees must either participate outside of work hours or take leave in order to receive compensation.

6 PARTICIPANT DISCONTINUATION/WITHDRAWAL

6.1 PARTICIPANT DISCONTINUATION/WITHDRAWAL FROM THE STUDY

Participants are free to withdraw from participation in the study at any time upon request.

An investigator may discontinue or withdraw a participant from the study for the following reasons:

- Significant non-compliance
- If the participant meets an exclusion criterion (either newly developed or not previously recognized) that precludes further study participation
- Subject has completed the study follow-up period
- Death
- Screen Failure

The reason for participant discontinuation or withdrawal from the study will be recorded on the Case Report Form (CRF).

6.2 LOST TO FOLLOW-UP

A participant will be considered lost to follow-up if he or she fails to return for two scheduled visits and is unable to be contacted by the study site staff.

The following actions must be taken if a participant fails to return to the clinic for a required study visit:

- The site will make one attempt to contact the participant and reschedule the missed visit within one week and counsel the participant on the importance of maintaining the assigned visit schedule and ascertain if the participant wishes to and/or should continue in the study.
- Before a participant is deemed lost to follow-up, the investigator or designee will make one attempt to regain contact with the participant either by email or telephone.
- Should the participant continue to be unreachable, despite this attempt, he or she will be considered lost to follow-up.

- It is possible that a participant deemed lost to follow-up will recontact the investigators to return to the study. In this case, if it is within six months of their consent date, they will be rescheduled. The subject will keep their previously assigned subject number.

7 STUDY ASSESSMENTS AND PROCEDURES

7.1 SCREENING PROCEDURES

7.1.1 Screening activities performed prior to obtaining informed consent

Minimal risk activities that may be performed before the subject has signed a consent include the following:

- Email, written, in person or telephone communications with prospective subjects.
- Review of existing medical records to include H&P, laboratory studies, etc.
- Review of existing MRI, x-ray, or CT images.

7.1.2 Screening activities performed after a consent for screening has been signed

The following activities will be performed only after the subject has signed the consent this study:

- Pregnancy test
- Clinical MRI scan, if none has been obtained within the last year

7.2 CLINICAL EVALUATIONS

MRI: 3T MRI will take an estimated 1 hour for baseline scanning.

MRI anatomical scanning: All participants will have anatomical (MPRAGE) scans at baseline. Participants who have not had one in the past year will receive a standard clinical MRI scan of the head, which will be submitted to the Diagnostic Radiology Department CC for interpretation. Depending on the requirement for a clinical scan, this phase will take 10-30 min.

Resting-state scanning: All participants will receive a resting-state fMRI scan at baseline for identification of a TMS target. During scanning, participants will be instructed to lie motionless with open eyes fixated on a cross that is presented on a screen visible through a mirror attached to the MR head coil (approximately 10 min).

Pregnancy testing: All participants of childbearing potential will undergo pregnancy testing before each MRI scan.

Assessment of adverse events will be monitored, tracked, documented, and reported by study investigators and the PI

7.3 BIOSPECIMEN EVALUATIONS

Not applicable

7.3.1 Correlative Studies for Research

Not applicable

7.3.2 Samples for Genetic/Genomic Analysis

Not applicable

8 STATISTICAL CONSIDERATIONS

8.1 STATISTICAL HYPOTHESIS

The primary aims are to investigate how TMS alters the EEG biomarkers of successful memory performance and how memory state-related neural changes influence plasticity of the brain. Secondary aims for this protocol will include examining the MRI connectivity predictors of TMS effects.

- Primary Objective 1: Investigate how TMS modulates EEG neural measures of successful memory and the relevance of modulation to behavioral performance
 - Hypotheses
 - a. Network-targeted parietal-TMS will improve memory performance (context recollection; Primary Endpoint 1) relative to vertex-TMS trials
 - b. Relative to vertex-TMS, parietal-TMS will also increase the Late Positive Posterior ERP (Primary Endpoint 2) and theta power (Primary Endpoint 3) during encoding on successful trials, relative to unsuccessful trials
 - c. Parietal-TMS will alter EEG functional connectivity patterns (Primary Endpoint 4) at encoding during successful trials relative to unsuccessful trials
 - d. The EEG effects will correlate with memory improvement (Correlation, Primary Endpoint 1 and 2-4)
 - e. Parietal-TMS will not influence neural activity or accuracy for spatial trials, relative to vertex-TMS and no-TMS
- Primary Objective 2: Examine how memory task state influences susceptibility to plasticity via TMS and determine the optimal neural state for improving memory
 - Hypotheses
 - a. Network-targeted parietal-TMS during memory encoding will have a larger effect on memory performance (Primary Endpoint 1), relative to pre-trial parietal-TMS and vertex-TMS during encoding
 - b. Exploratory Analyses:
 - i. Parietal-TMS during memory encoding will increase the Late Positive Posterior ERP (Primary Endpoint 2) and theta-power (Primary Endpoint 3), relative to pre-trial parietal-TMS and vertex-TMS during encoding
 - ii. Additionally, parietal-TMS will alter EEG functional connectivity patterns (Primary Endpoint 4) during later-remembered trials, relative to pre-trial parietal-TMS and vertex-TMS during encoding
 - iii. Network-targeted TMS will not influence neural activity during arithmetic trials, relative to vertex-TMS and no-TMS

- *Exploratory Objective:* Determine MRI predictors of the effects of noninvasive stimulation
We will examine the correlations between stimulation effects on our behavioral and neural outcome measures (Primary Endpoint 1 and Primary Endpoints 2-4) and MRI measures of structural and functional connectivity (Exploratory Endpoints 1-2). For each participant, the Pearson correlation between (1) the difference in outcome measures paired with parietal-TMS and vertex-TMS and (2) hippocampal FA or hippocampal functional connectivity will be calculated. Thresholds for significant effects will be set at $p<0.05$ following FDR correction for multiple comparisons.

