8.2 SAMPLE SIZE DETERMINATION

All experiments in this protocol are powered based on the primary outcome, which relates to the effects of TMS on memory and its neural correlates.

A power analysis was conducted using G*Power v3.1.9.7. We used a repeated-measures, within-factors ANOVA based on a previous study with a similar design³⁹. Like the proposed experiments, this study delivered 2-second trains of TMS prior to trials of memory encoding or a control task and examined the effects on later memory performance and on neural activity, in this case hippocampal fMRI activity, during encoding. They used a three-way repeated-measures ANOVA to examine the interactions between TMS presence (on vs off), frequency (theta-burst vs 12.5 Hz beta), and location (parietal cortex vs supplementary motor area) and found an effect size of theta burst parietal-TMS on memory performance of $\eta^2=0.44$ and fMRI hippocampal activity of $\eta^2=0.28$. As the proposed analyses will also use three-way repeated-measures ANOVAs (see Section 8.3.2), we calculated subject number based on these effect sizes, power of 0.80, and $\alpha = 0.05$ shared across two primary outcomes, memory performance and the late positive posterior ERP ($\alpha = 0.025$ for each outcome). Thirty-two participants with complete data will be needed. To achieve $n=32$, we will recruit up to 50 subjects to account for potential non-completion (e.g., screen failure, subject withdrawal) or unusable data (e.g., due to noise).

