8.3.2 Analysis of the Primary Endpoints

- Primary Endpoint 1: Investigate how TMS modulates EEG neural measures of successful memory and the relevance of modulation to behavioral performance
This aim will examine behavioral and EEG neural outcome measures (Primary Endpoints 1-4). We will perform 3x3 ANOVAs on each outcome measure with the factors trial type (successful/ unsuccessful/ spatial), stimulation site (parietal/ vertex/ none), and their interaction. We will particularly focus on the main effect of stimulation site to determine

the influence of parietal-TMS on memory performance and its neural correlates, and the interaction effect to determine the task specificity of TMS effects. Thresholds for significant effects will be set at $p<0.025$ following FDR correction for multiple comparisons.

- Primary Endpoint 2: Examine how memory task state influences susceptibility to plasticity via TMS and determine the optimal neural state for improving memory
This aim will examine behavioral and EEG neural outcome measures (Primary Endpoints 1-4). We will perform 3x3x2 ANOVAs on each outcome measure with the factors trial type (successful/ unsuccessful/ spatial), stimulation site (parietal/ vertex/ none), stimulation timing (pre-trial and mid-trial) and their interaction. We will particularly focus on the interaction effect of stimulation site and timing to determine the influence of memory task-state parietal-TMS on memory performance and its neural correlates, and the three-way interaction effect to determine the task specificity of state-dependent TMS effects. Thresholds for significant effects will be set at $p<0.025$ following FDR correction for multiple comparisons.

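### The trial type by site interaction cannot show that spatial trials are spared, and the hypothesis of no effect on them has no contrast or criterion of its own

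*Combined protocol and SAP*

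**What the plan says.** Hypothesis e under Primary Objective 1 (Section 8.1, repeated in Section 4) is a statement of no effect: "Parietal-TMS will not influence neural activity or accuracy for spatial trials, relative to vertex-TMS and no-TMS". It has two comparators and two kinds of outcome. A companion exploratory statement under Primary Objective 2 reads "Network-targeted TMS will not influence neural activity during arithmetic trials, relative to vertex-TMS and no-TMS"; no arithmetic task is described elsewhere in the protocol.

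The analysis in Section 8.3.2 is a 3x3 ANOVA "with the factors trial type (successful/ unsuccessful/ spatial), stimulation site (parietal/ vertex/ none), and their interaction". It looks to the site main effect for the influence of parietal stimulation, and to "the interaction effect to determine the task specificity of TMS effects". The 3x3x2 model for the second objective uses "the three-way interaction effect to determine the task specificity of state-dependent TMS effects". The only decision rule is "Thresholds for significant effects will be set at $p<0.025$ following FDR correction for multiple comparisons".

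Section 8.2 sizes the study to detect differences. An alpha of 0.05 is "shared across two primary outcomes, memory performance and the late positive posterior ERP", giving 0.025 each, and "we calculated subject number based on these effect sizes, power of 0.80". The effect sizes are eta-squared 0.44 (memory performance) and 0.28 (hippocampal fMRI activity), both from one earlier study. The result is 32 participants with complete data.

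The Spatial Task description in Section 4 gives that task the role of separating hippocampal-network effects from local effects at the stimulated site. It also notes that spatial processing itself engages posterior parietal cortex.

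**The concern.** Task specificity needs a comparison of the site effect on memory trials with the site effect on spatial trials. The planned interaction mixes that comparison with another: whether the site effect differs between successful and unsuccessful memory trials. Hypothesis b under Primary Objective 1 predicts that second difference for the ERP and theta power. If it exists, the interaction can be significant whatever happens on spatial trials.

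Hypothesis e is a separate problem. The site main effect pools spatial with memory trials, so no planned term isolates the site effect on spatial trials, and nothing states what result would support absence of effect. The accuracy half is covered even less. Success is a level of the trial-type factor, so accuracy cannot be the outcome of that ANOVA as written, and match/no-match accuracy is not an endpoint in Section 3.

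At stake is the mechanistic claim. Because the control task engages the stimulated region, a local effect on spatial trials is a real possibility that the analysis should be able to show or bound.

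**Working it through.** **The plan's sample size.** Inputs from Section 8.2: eta-squared 0.28, alpha 0.025, power 0.80. f² = 0.28/(1 − 0.28) = 0.389, so f = 0.624. For a three-level within-subject factor with df 2 and 2(N − 1) and noncentrality f²N, the smallest N with 80% power is 32, which reproduces the plan. The match is not unique, because the documents do not give the number of measurements, the correlation or the effect-size option. A 1-df effect, for example, gives N = 28. Every variant concerns detecting a difference.

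**Degrees of freedom.** Two-way interaction: (3 − 1)(3 − 1) = 4. Three-way interaction: 2 × 2 × 1 = 4.

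**What the interaction responds to.** Simulated 3x3 repeated-measures ANOVA with n = 32, alpha 0.025 and independent residuals. Effects are parietal versus control, in SDs of the paired difference (dz). The effect values and residual structure are assumptions.

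| True effect: successful / unsuccessful / spatial | Interaction significant |
|---|---|
| 0.8 / 0 / 0.4 | 76% |
| 0.5 / 0.5 / 0.5 | 2.3% |
| 0 / 0 / 0.3 | 13% |

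In the first row the average memory effect is (0.8 + 0)/2 = 0.4, equal to the spatial effect. There is no memory-versus-spatial difference and spatial trials are affected, yet the interaction is usually significant. A 1-df contrast of average memory effect minus spatial effect was significant in 2.6% of runs, close to the nominal 2.5%. In the third row a spatial-only effect is missed in 87% of runs. Neither a significant nor a non-significant interaction settles whether spatial trials are spared.

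**What a non-significant spatial contrast would mean.** Assumption: f is read as the dz of a paired parietal-versus-control contrast. Power comes from the noncentral t with 31 df and noncentrality dz√32, two-sided alpha 0.025.

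- Eta-squared 0.28: f = 0.624, half is 0.312, noncentrality 1.76, power 0.29, missed 71%.
- Eta-squared 0.44: f = √(0.44/0.56) = 0.886, half is 0.443, noncentrality 2.51, power 0.57, missed 43%.

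The matching 97.5% confidence interval has half-width t(0.9875, 31)/√32 = 2.356/5.657 = 0.42 SD of the paired difference.

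**What n = 32 can exclude.** Two one-sided tests on one paired comparison, by simulation. The documents give no margin, so all margins are assumptions.

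| Quantity | One-sided 0.05 | One-sided 0.025 |
|---|---|---|
| Smallest margin with 80% power, true difference 0 | 0.53 SD | 0.59 SD |
| Equivalence declared, margin 0.62, true dz 0.31 | 53% | 40% |

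Requiring equivalence to both vertex-TMS and no-TMS lowers the power further.

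**The case against.** A reader might infer that the investigators will read p above 0.025 on spatial trials as proof of no influence. No section says so. Section 8.3.2 ties specificity to the interaction, which implies a significant result. The defect is that the interaction does not isolate the comparison and that hypothesis e has no criterion, not that a faulty criterion is written down. This objection stands.

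A reader might also take the 71% miss rate as the size of the problem. It is one end of a range. It halves the effect from eta-squared 0.28, a hippocampal fMRI result from another study; halving the memory-performance effect gives 43%. The conversion to a paired effect is itself an assumption, since the documents state neither the degrees of freedom nor the type of eta-squared. This stands too.

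A third inference would be that an equivalence test at the planning effect (0.62) cures the problem. It does not: it would still declare equivalence in 40% to 53% of trials when the true effect is half that size.

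On weight, hypothesis e is a supporting control and not one of the two powered outcomes, and an analyst may well inspect the pattern of means after a significant interaction. That limits the severity. It does not supply the missing contrast, because the plan names no follow-up.

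**Conclusion.** The point holds in this form. The 4-df interaction is the wrong test of task specificity: it was significant in 76% of simulated trials with no memory-versus-spatial difference on average, given the assumed effects and independent residuals. Hypothesis e has neither a spatial-trial contrast nor a criterion, and the sample size gives no assurance for it. A non-significant spatial result at n = 32 would be weak evidence, with a half-size effect missed in 43% to 71% of trials. The miss rates use an unadjusted alpha of 0.025, and FDR adjustment could only raise them. The documents do not support saying that the plan equates non-significance with absence of effect. The change should be made before analysis, but it does not affect the sizing of the two powered outcomes.

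**What to change.** 1. For the EEG outcomes, replace the omnibus interaction as the specificity test with one planned 1-df contrast: (parietal minus vertex on memory trials) minus (parietal minus vertex on spatial trials). State how successful and unsuccessful trials are weighted in the memory average. Do not apply this contrast to behaviour: memory accuracy and match/no-match accuracy are different measures without a common scale.
2. Report the spatial-trial parietal-minus-vertex and parietal-minus-no-TMS differences with confidence intervals, for EEG and separately for match/no-match accuracy.
3. Either reword hypothesis e as a larger effect on memory than on spatial trials, or claim absence of influence only when the interval lies within a pre-stated, justified margin. State that n = 32 can exclude only large effects: margins of about 0.53 to 0.59 SD for 80% power on one comparison if the true difference is zero.
4. Reconcile the reference to arithmetic trials with the spatial task.

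The cost is SAP wording and a few contrasts, with no new participants or procedures. The claim of no influence becomes harder to make and is limited to ruling out large effects. The memory average also dilutes an effect confined to successful trials: with equal weights, 0.5 on successful trials alone becomes (0.5 + 0)/2 = 0.25.

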8.2 SAMPLE SIZE DETERMINATION

All experiments in this protocol are powered based on the primary outcome, which relates to the effects of TMS on memory and its neural correlates.

A power analysis was conducted using G*Power v3.1.9.7. We used a repeated-measures, within-factors ANOVA based on a previous study with a similar design³⁹. Like the proposed experiments, this study delivered 2-second trains of TMS prior to trials of memory encoding or a control task and examined the effects on later memory performance and on neural activity, in this case hippocampal fMRI activity, during encoding. They used a three-way repeated-measures ANOVA to examine the interactions between TMS presence (on vs off), frequency (theta-burst vs 12.5 Hz beta), and location (parietal cortex vs supplementary motor area) and found an effect size of theta burst parietal-TMS on memory performance of $\eta^2=0.44$ and fMRI hippocampal activity of $\eta^2=0.28$. As the proposed analyses will also use three-way repeated-measures ANOVAs (see Section 8.3.2), we calculated subject number based on these effect sizes, power of 0.80, and $\alpha = 0.05$ shared across two primary outcomes, memory performance and the late positive posterior ERP ($\alpha = 0.025$ for each outcome). Thirty-two participants with complete data will be needed. To achieve $n=32$, we will recruit up to 50 subjects to account for potential non-completion (e.g., screen failure, subject withdrawal) or unusable data (e.g., due to noise).

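### The 0.80 power behind N = 32 makes no allowance for averaging the Objective 1 site effect over spatial trials, so ERP power for that main effect is likely, though not certainly, below 0.80

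*Combined protocol and SAP*

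**What the plan says.** Section 8.2 takes two effect sizes for theta-burst parietal-TMS from an earlier three-way study: eta-squared 0.44 for memory performance and 0.28 for hippocampal fMRI activity. Its reason for using them is: "As the proposed analyses will also use three-way repeated-measures ANOVAs (see Section 8.3.2), we calculated subject number based on these effect sizes, power of 0.80". Alpha is 0.05 split over two primary outcomes, memory performance and the late positive posterior ERP, so 0.025 each. The result is 32 participants with complete data. The section gives no ERP effect size, numerator df, correlation among repeated measures or G*Power effect-size option.

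For Objective 1, Section 8.3.2 says: "We will perform 3x3 ANOVAs on each outcome measure with the factors trial type (successful/ unsuccessful/ spatial), stimulation site (parietal/ vertex/ none), and their interaction". On interpretation it says "We will particularly focus on the main effect of stimulation site to determine" how parietal-TMS affects memory performance and its neural correlates. The same sentence names a second focus, the site-by-trial-type interaction, for task specificity. For Objective 2 the model is a three-way 3x3x2 ANOVA that adds stimulation timing.

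In Section 8.1, hypothesis 1b predicts an ERP increase under parietal-TMS, relative to vertex-TMS, on successful compared with unsuccessful encoding trials. Hypothesis 1e states: "Parietal-TMS will not influence neural activity or accuracy for spatial trials, relative to vertex-TMS and no-TMS". Under Objective 2 the ERP predictions are listed as exploratory.

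**The concern.** The reason given for carrying over the effect sizes does not fit the analysis in which the non-exploratory ERP hypothesis is tested. Objective 1 is a two-way model, and the term assigned to the neural correlates is a main effect averaged over three trial types. By hypothesis 1e, one of the three carries no effect. If the gain is confined to successful trials, two of the three carry none. Section 8.2 describes 0.28 as an effect on neural activity during encoding and does not adjust it for this averaging.

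At stake is how a null ERP result would be read. The late positive ERP is one of two outcomes sharing alpha, and a non-significant site main effect would be interpreted as if power had been 0.80.

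**Working it through.** **Inputs.** Eta-squared 0.28, alpha 0.025, power 0.80 and N = 32 come from Section 8.2. The models and focus tests come from 8.3.2, and the predicted pattern of effects from 8.1. The correlation r between trial types in the site-by-subject error is not in the documents, so it is run from 0 to 1. Sphericity is assumed, with no further loss from the FDR step.

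**Reproducing N = 32.** f² = 0.28/0.72 = 0.389. With a three-level within factor, df = 2 and 2(N − 1), and noncentrality λ = f²N:
- N = 31: λ = 12.06, power 0.793.
- N = 32: λ = 12.44, F(2, 62), power 0.809.

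This match was found by search, since the settings are not stated. A 1-df version needs 28. The 2-df version with λ = f² × df2 needs 18. Memory (0.44) in the matching version needs only 17, so the ERP drives the sample size.

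**Two scalings.** Scaling A is the matching one, λ = f²N. Scaling B reads 0.28 as a 1-df parietal-versus-control difference with vertex equal to no stimulation. The 2-df site test then has λ = (4/3)f²N. Without dilution, N = 32 gives λ = 16.6 and power 0.92.

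**Dilution.** Averaging over three trial types multiplies the squared mean effect by (2/3)² = 4/9 if both memory levels respond equally, or (1/3)² = 1/9 if only successful trials respond. It also changes the error variance to (1 + 2r)/3 of a single cell. The multiplier on λ is:
- Case 1, both memory levels respond and 0.28 describes pooled memory trials: (4/9) × [(1 + r)/2] / [(1 + 2r)/3].
- Case 2, both respond and 0.28 describes a single trial-type cell: (4/9) × 3/(1 + 2r).
- Case 3, only successful trials respond, single-cell reference: (1/9) × 3/(1 + 2r).

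Power of the 3x3 site main effect for the ERP at N = 32, alpha 0.025:

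| Case | r | Multiplier | Scaling A | Scaling B |
|---|---|---|---|---|
| 1 | 0 | 0.667 | 0.60 | 0.75 |
| 1 | 0.5 | 0.500 | 0.46 | 0.60 |
| 1 | 1 | 0.444 | 0.41 | 0.54 |
| 2 | 0 | 1.333 | 0.92 | 0.98 |
| 2 | 1/6 | 1.000 | 0.81 | 0.92 |
| 2 | 0.4 | 0.741 | 0.66 | 0.80 |
| 2 | 0.5 | 0.667 | 0.60 | 0.75 |
| 2 | 1 | 0.444 | 0.41 | 0.54 |
| 3 | 0 | 0.333 | 0.30 | 0.41 |
| 3 | 0.5 | 0.167 | 0.15 | 0.20 |
| 3 | 1 | 0.111 | 0.10 | 0.13 |

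**The other named test.** Putting 0.28 on the 4-df interaction, with λ = f²N = 12.44 and F(4, 124), gives power 0.71.

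**Memory trials only.** If 0.28 describes pooled memory trials, the site test on those trials is undiluted: 0.81 under A, 0.92 under B. If only successful trials respond, with a single-cell reference, the multiplier is (1/4) × 2/(1 + r). Power then falls from 0.46 (r = 0) to 0.22 (r = 1) under A, and from 0.60 to 0.30 under B. Pooling memory trials therefore does not by itself serve hypothesis 1b.

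**The case against.** The strongest reply is that the site main effect is not the only Objective 1 test. Section 8.3.2 also names the interaction, and hypothesis 1b is itself a site-by-trial-type statement. The interaction is not weakened by averaging over spatial trials, so a null main effect need not decide the ERP question. This stands. But 8.3.2 gives the interaction a different purpose, task specificity, and 8.2 does not show that it is powered.

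Second, averaging over three trial types also reduces error variance. In case 2 with low r the main effect keeps power at or above 0.80. This stands too. A reader might infer that the 0.80 is definitely not delivered. The documents do not support that, because they give neither r nor the term behind 0.28, which could be a simple effect, an interaction or a partial eta-squared.

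Third, a reader might infer that 32 is an arithmetic error, or that the three-way wording is simply wrong. Neither follows. The figure reproduces with the df of a three-level site factor, and the wording is right for Objective 2.

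Fourth, case 3 is an extreme reading. Hypothesis 1b predicts a larger gain on successful trials, not zero gain on unsuccessful ones. The lowest figures therefore mark a bound.

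Finally, under the software option with λ = f² × df2, case 1 power would be 0.74 to 0.91. That option does not reproduce 32.

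**Conclusion.** The point holds in a conditional form. Section 8.2 justifies its effect sizes by a model that Objective 1 does not use. It also makes no allowance for including spatial trials, for which the plan predicts no effect, in the site main effect. The reproduced calculation has under one percentage point to spare for the ERP, so most of the plausible settings examined take that main effect below 0.80:
- about 0.41 to 0.60 (0.54 to 0.75 under scaling B) if both memory levels respond and 0.28 describes pooled memory trials;
- 0.41 to 0.92 (0.54 to 0.98) if 0.28 describes a single cell, reaching 0.80 only for r up to about 1/6 (about 0.4);
- about 0.10 to 0.41 across both scalings if only successful trials respond.

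These figures assume that the imported fMRI effect size carries over to the ERP, as 8.2 does. FDR correction at 0.025 over a family that 8.3.2 leaves undefined could lower them and would not raise them.

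**What to change.** In Section 8.3.2, test the ERP effect of parietal-TMS on memory-encoding trials only. Specify the site effect on those trials and, for hypothesis 1b, the contrast of parietal versus vertex by successful versus unsuccessful. Use spatial trials only in the task-specificity comparison.

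In Section 8.2, limit the three-way wording to Objective 2, and name the term and df to which the 0.80 applies. If the 3x3 site main effect remains the focal test, replace the flat 0.80 for the ERP with its power under hypotheses 1b and 1e, and state the assumed correlation between trial types.

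The cost is wording in two sections, with no added participants or procedures; N stays at 32. The downside is a less favourable stated power if the main effect is kept.

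### Once one test per primary outcome is named, Holm at 0.05 improves on the flat 0.025 split: late positive ERP power rises from about 0.81 to about 0.88 if the planned memory effect holds

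*Combined protocol and SAP*

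**What the plan says.** Section 8.2 describes the calculation: "We used a repeated-measures, within-factors ANOVA based on a previous study with a similar design". It quotes two effect sizes from that study, eta-squared 0.44 for memory performance and 0.28 for hippocampal fMRI activity, and continues: "we calculated subject number based on these effect sizes, power of 0.80". Alpha 0.05 is "shared across two primary outcomes, memory performance and the late positive posterior ERP", at 0.025 each. The result is: "Thirty-two participants with complete data will be needed". No step-down or passing on of unused alpha is mentioned.

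Section 8.3.2 gives the analysis rule. Effects count as significant at p<0.025 "following FDR correction for multiple comparisons". This applies to Primary Endpoints 1 to 4, to a 3x3 ANOVA for the first objective and a 3x3x2 ANOVA for the second, with a main effect and several interactions singled out. The set of tests that the FDR correction covers is not stated.

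Elsewhere the family of primary outcomes looks like two. The synopsis and Section 3 mark theta/alpha power and EEG connectivity as secondary, and the objectives in Section 4 call connectivity exploratory.

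**The concern.** With two tests and a family-wise level of 0.05, a flat split is never better than Holm. Holm compares the smaller p-value with 0.025 and, if that passes, the larger with 0.05. On the plan's own inputs memory is the easy outcome and the ERP the hard one, so the ERP would usually be judged at 0.05 under Holm. The flat split holds it to 0.025 and gains nothing in the family-wise level for it. Section 8.3.2 goes further, correcting again from a threshold that has already been halved. At stake is avoidable loss of power on the harder primary outcome.

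**Working it through.** **Inputs.** From 8.2: eta-squared 0.44 (memory) and 0.28 (used for the neural outcome), alpha 0.025 each, power 0.80, N = 32. From 8.3.2: three stimulation sites, hence 2 numerator df for the site effect. Assumed, because the G*Power options are not stated: noncentrality λ = f²·N with f² = η²/(1−η²), and denominator df 2(N−1).

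**Reproducing N = 32.** f² for 0.28 is 0.28/0.72 = 0.389, so λ = 0.389 × 32 = 12.44. At alpha 0.025 with F(2, 62), power is 0.809; N = 31 gives 0.793. The smallest N reaching 0.80 is therefore exactly 32, which suggests that the smaller effect sets the sample size. For memory, f² = 0.44/0.56 = 0.786, λ = 25.14, and power at 0.025 is 0.989.

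**Error control.** If both nulls are true, Holm errs only when the smaller p-value is at or below 0.025, which has probability at most 0.025 + 0.025 = 0.05. If one null is true, its p-value must be at or below 0.05. So the bound of 0.05 holds under any dependence. With both nulls true, simulated error is 0.049 at correlation 0 and 0.040 at correlation 0.8, identical to the flat split.

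**No loss of power.** Any p-value at or below 0.025 is rejected by Holm: either it is the smaller one, or the smaller one has also passed 0.025. Holm therefore rejects whatever the flat split rejects, and whatever Benjamini-Hochberg at 0.025 rejects among these two tests.

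**ERP power at N = 32.** For independent tests, Holm power = P(0.025) + [P(0.05) − P(0.025)] × memory power, where P(a) is ERP power at level a.

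- Flat split: 0.809.
- Holm: 0.809 + (0.879 − 0.809) × 0.989 = 0.878.
- Benjamini-Hochberg at 0.025 over the two outcomes: 0.727 + (0.809 − 0.727) × 0.989 = 0.808.
- Benjamini-Hochberg at 0.025 over four endpoints, with effects only in memory and the ERP: the ERP must reach about 0.025 × 2/4 = 0.0125, where power is about 0.73.

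**Dependence on memory.** Starting from exactly 0.80 at 0.025 (λ = 12.21, F(2, 62)), ERP power at 0.05 is 0.872. Holm power is then 0.80 + 0.072 × memory power if the tests are independent. The last column is a simulation under a normal approximation.

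| Memory power at 0.025 | ERP power under Holm, independent | ERP power under Holm, correlation 0.5 |
|---|---|---|
| about 0.99 (planned effect) | 0.87 | 0.87 |
| 0.80 | 0.86 | 0.85 |
| 0.50 | 0.84 | 0.82 |
| 0.025 (no effect) | 0.80 | 0.80 |

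**Sensitivity to the model.** With eta-squared 0.28 and N = 32, a 1-df test gives 0.873 under the flat split and 0.927 under Holm. A multivariate F with 2 and 30 df gives 0.778 and 0.859. Neither reproduces N = 32: they need 28 and 34 participants.

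**The case against.** The strongest reply is that the flat split is only a sample-size input. Section 8.3.2 sets a different rule, FDR-corrected over four endpoints and several effects, so 0.80 is not the ERP's power under the analysis as written. This stands. A reader might infer that the plan tests the ERP at a plain 0.025 and that swapping in Holm lifts 0.80 to 0.87. The documents do not support that, because no single memory or ERP test is named. Section 3 lists item accuracy, context accuracy and d' for memory, and both encoding and retrieval for the ERP. The hypotheses in 8.1 point to context recollection and to encoding, but 8.3.2 does not carry that through to one effect. Naming the tests comes first, and Holm is a refinement after that.

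A reader might also infer that the gain is unconditional. It depends on memory passing 0.025, and the planned memory effect comes from one earlier study. The ERP's absolute power is uncertain too: 0.28 is an fMRI effect, and 8.2 states 0.80 once, not for the ERP specifically. Nor may a starting power of 0.80 be paired with a 1-df test at eta-squared 0.28, since that test already has 0.873 at N = 32.

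Finally, an equal split is valid and conservative, and under the reproducing model it meets the 0.80 target. That is right, and it limits the point to efficiency. It does not show any advantage of the split in power or in the family-wise level. Its one advantage is that matching simultaneous confidence intervals are simpler.

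**Conclusion.** The point holds as a cheap improvement. Nothing in the plan's figures is wrong, and N = 32 reproduces. For two named tests, Holm at 0.05 is never less powerful than the flat split or Benjamini-Hochberg at 0.025, with family-wise error at or below 0.05 under any dependence; this needs no assumption about effect sizes.

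The size of the gain does need assumptions. It is about 7 points of ERP power under the 2-df model with the planned memory effect, less if memory is weaker, and essentially nil if memory has no effect. Across the three models, ERP power at N = 32 is 0.78 to 0.87 under the flat split and 0.86 to 0.93 under Holm. Against the rule in 8.3.2, the comparison is with about 0.81 if FDR spans two outcomes, or about 0.73 if it spans four with effects only in memory and the ERP (Benjamini-Hochberg assumed).

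**What to change.** - In 8.3.2, name one memory test and one late positive ERP test as confirmatory. For each, give the measure, the phase (encoding or retrieval), the objective and the ANOVA effect or contrast.
- In 8.2 and 8.3.2, for those two tests only, replace the 0.025 per outcome and the FDR-corrected 0.025 by Holm-adjusted p<0.05.
- Keep FDR for the remaining endpoints and effects, and state which tests it covers.
- Keep N = 32. State the G*Power options and the df of the named tests, and give ERP power as conditional on the memory effect, for example as in the table above.

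The Holm change is a few sentences. Naming the two tests takes more thought, but the plan needs it under any multiplicity rule. No participants or procedures are added. The small cost is that simultaneous confidence intervals matching Holm decisions are less simple; nominal intervals, labelled as such, can be reported. The change should be fixed before outcome data are analysed.
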